Although non-inferiority is an acceptable outcome for the improvised dressing, the review of the literature supports the expectation that it will outperform usual practice. This superiority study design eliminate the motive for the blinded evaluators to minimize differences between groups, biasing the results.¹³ If superiority is attained, the results will be evaluated with intent to treat (ITT) analysis.

If superiority is not demonstrated, the data for the improvised dressing and usual practice dressing will be re-evaluated to assess for noninferiority.¹³ Contrary to superiority trials where use of intention-to-treat is employed to protect against type 1 error, the appropriate approach for noninferiority trials is to use a per-protocol approach,¹³ which, at worst, would exaggerate the differences between treatment groups, thereby yielding a more conservative estimate in the setting of a noninferiority trial.¹³ Thus, only those patients completing treatment in the group to which they were randomized will be retained for any non-inferiority analyses (see appendix for further details).

b. Study population

Individuals diagnosed with sickle cell disease who have a SCLU and reside in the parishes of St. Catherine, St. Andrew, or Kingston parishes of Jamaica and respond to advertisements, recruitment phone calls, or flyers posted at the Sickle Cell Unit (SCU) clinic and UHWI prior to and during the enrollment period will be invited to participate in the study. Members of the UHWI surgical team will call all patients identified by the SCU as having had a SCLU within the past two years to invite them to participate in the study. Jamaican residents who otherwise qualify but who live outside the study area will be included only if they agree to provide their own transportation and faithfully attend all clinic visits.

c. Sample

Study participants must have HbSS or HbS β^0 sickle cell disease, be between the ages of 13 and 70, and have a chronic SCLU, defined as a wound in a patient with sickle cell disease that has been open for at least one month and is below the knee, excluding the plantar surface of the foot. All SCLUs on a single patient will be dressed with the same dressing protocol. The largest ulcer at initial presentation is the study SCLU. If two or more SCLUs in close proximity join into

an enlarged ulcer during the first four weeks of the study, the sum of the initial areas will be considered the initial wound size for calculation purposes.

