Decrease in SCLU surface area will be used to answer research question 1. Conducting a power analysis for this study is challenging because only one study of SCLUs has demonstrated a statistically significant outcome, and the effect size was obscured by high standard deviations, which is a common problem in studies of wounds.⁸ Improvised plastic dressings similar to the study dressings were used in 49 chronic pressure ulcers in elderly patients, which are often slow to close, if they heal at all.⁶⁰ These two studies demonstrated a significant difference with confidence intervals of 99% with ~25 patients per group. Based upon these sample sizes and the Central Limit Theorem, it is reasonable to set the minimum sample size for this study at 30 patients per group,.^{88,89}

d. Variables

Dependent Variables (measured weekly - tools and permissions in appendices):

- 1. Persistent wound pain (using the Faces Pain Scale Revised (FPS-R))
- 2. Procedural (dressing change) wound pain
- 3. Amount of pain medication taken, including a total number of morphine equivalents plus non-opioid pain medications
- 4. Approximate time spent standing, or sitting with leg dependent without compression (estimated hours per week)
- 5. Patient overall quality of life (assessed with the ASCQ-Me Emotional, Pain, Social Functioning, Stiffness, and Sleep Impact Short Forms)
- 6. Patient wound-specific quality of life (assessed with the Wound QoL tool)
- 7. Materials costs (estimated, using lowest retail costs on Amazon.com for items not on the UWI price sheets)
- 8. Time spent performing dressing changes
- 9. Wound complication rates (e.g., wound infection, healing impairing maceration, wound deterioration)
- 10. Change in wound surface area (measured in cm² electronically using software that automatically corrects for skew, such as HealthEPix or WoundMatrix)⁹⁰

Dependent Variables (measured one time, at graduation from study)

- 11. Wound closure time, in weeks (see definitions; verified two weeks later. Omit patients whose wounds did not fully close they are included in 10., above.)
- 12. Acceptability of dressing choice patient (5 point Likert scale and qualitative free response)
- 13. Acceptability of dressing choice family member (5 point Likert scale and qualitative free response)
- 14. Acceptability of dressing choice UHWI staff (5 point Likert scale and qualitative free response)

Independent Variables (documented at initial study visit):

1. Patient gender

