- Based upon previous studies and the Central Limit Theorem, an estimated 90 participants (~30 per group) may be required for the differences between groups to reach statistical significance.^{12,23,88,89,96} Up to 120 patients will be recruited to allow for a 25% dropout rate. Based upon the literature review, pain, costs, wound size, and quality of life are expected to be significantly improved using the improvised dressings. However, because SCLUs are, historically, very slow to heal and often enlarge, complete wound closure is not an expected outcome for all patients.

g. Procedures for recruitment and consent

The study will be advertised using free community information channels such as church bulletins and radio outlets. Social media sites such as the CAIHR Facebook page will also be employed. Qualifying patients in the SCU database from up to two years prior to the study initiation will be called by the UHWI surgical team, alerting them to the dates for registering to participate. Flyers will be posted at the SCU in advance. Consent will be obtained by a member of the research team while the potential participant is waiting to be seen for wound care.

h. Data collection

The site for this study is the surgical clinic dressing area at the University Hospital of the West Indies (UHWI), Mona, Jamaica. The adjacent Sickle Cell Unit (SCU) will refer any SCLU patients to UHWI during the study period. UHWI is consistently well staffed with competent Jamaican health professionals. The UHWI surgical team will lead the study. Relatively few Jamaicans live or work in air-conditioned environments, ^[data in appendices] allowing the results from this out-patient population to translate to less developed tropical countries.

To ensure consistency, members of the research team will practice until they can demonstrate competency with all three dressing change procedures and with explaining the study forms prior to study patient recruitment.

Enrollment in the study will begin within two weeks of the day the Principal Investigator arrives at the Mona campus and will close 60 days later, or when a maximum of 120 patients have enrolled. All sickle cell positive patients presenting to UHWI with lower leg ulcers during the enrollment period will be screened for eligibility to enter the study. Each patient's data will be recorded for a total of 12 weeks, or until their SCLU has been closed for 2 weeks, whichever comes first.

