Patients (and adult relatives of eligible patients under the age of 18) will have the study explained to them by one of the members of the UHWI surgical team. Questions will be addressed thoroughly. Families will be assured that if they choose not to participate in the study, the SCLU will be managed with usual practice. The patient (and a decision-maker of the family, in the case of a minor) must sign the consent for the patient to be enrolled in the study.

Immediately after consent is obtained, the study tools (Patient Data Collection sheet, Faces Pain Scale – Revised (FPS-R), ASCQ-Me, and Wound QoL) will be explained to the patient and family. Baseline persistent pain will be assessed using the Faces Pain Scale – Revised (FPS-R).

All of the initial independent variable data will be handwritten onto the patient's individual Study Data Collection Form upon enrollment in the study. The largest SCLU upon initial presentation is the study wound. All SCLUs will be measured for the first four weekly visits to UHWI. If two or more SCLUs in close proximity join during the first four weeks, the sum of the initial areas will be the initial wound size.

The SCLU(s) will be measured initially by placing two pieces of clear plastic on top of one another and tracing the wound edges. The plastic that came in contact with the wound(s) will be discarded and the plastic with the markings on it will be added to the patient's documentation so that the patient can be shown if the SCLU is becoming smaller at subsequent dressing changes. SCLU area will be measured in cm² electronically from a photo, using software such as HealthEPix or WoundMatrix.

Patients (with the support of their families) will be taught to evaluate and document persistent and dressing change pain, pain medication doses taken, time spent and supplies used at dressing changes, their activity, and their use of compression on a checklist-style Study Continuation Form daily. They will either provide the research team with their weekly summary and wound photo via WhatsApp, or they will attend the clinic weekly so that the research team can obtain this data. Two encrypted USB drives containing the data, including wound photographs, will be updated weekly on an alternating schedule and stored in a securely locked file in the UHWI surgical clinic dressing area, along with the paper study documentation.

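### The correction for merging ulcers stops at week 4 of a 12-week follow-up, so as written a later join counts the neighbouring ulcer's area as growth

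*Combined protocol and SAP*

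**What the plan says.** Section 3c (Sample) sets the unit of measurement: "The largest ulcer at initial presentation is the study SCLU". It makes one exception, for neighbouring ulcers that merge within four weeks of the start: "the sum of the initial areas will be considered the initial wound size for calculation purposes". Section 3h (Data collection) gives the same rule with the same limit: "If two or more SCLUs in close proximity join during the first four weeks, the sum of the initial areas will be the initial wound" (cut before its last word).

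On measurement, section 3h says "The SCLU(s) will be measured initially by placing two pieces of clear plastic on top of one another and tracing the wound edges", and then "All SCLUs will be measured for the first four weekly visits to UHWI". Nothing requires ulcers other than the study ulcer to be measured after that.

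On follow-up, each patient's data "will be recorded for a total of 12 weeks", or until the ulcer has been closed for two weeks if that is sooner. On use, section 3c says "Decrease in SCLU surface area will be used to answer research question 1". In section 3d, change in area is dependent variable 10, measured weekly in cm². Initial area is independent variable 7, with a pointer to the rule for adjacent ulcers, and section 3i uses the independent variables as ANCOVA covariates.

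No section says how a join in weeks 5 to 12 is scored.

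**The concern.** The same event gets two different scores depending on the week in which it happens. By week 4 the baseline covers both ulcers. From week 5 the default baseline of one ulcer remains, while the traced wound now contains two. Skin that was already ulcerated at entry is then recorded as new growth, and a patient whose combined area has shrunk can be recorded as worse.

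Area change carries research question 1, and section 3c already notes that high standard deviations obscure effects in wound studies. Added noise makes superiority harder to show. It also makes it easier to meet the plan's definition of effective (section 2), which asks only that results be not significantly worse than usual practice.

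A second issue is the covariate. Independent variable 7 takes its value from the merge rule, so a nominal baseline covariate can be changed by an event after randomisation that the dressing might influence.

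**Working it through.** **1. The plan's own figure.** Section 3f: 90/(1 − 0.25) = 120, as stated. This confirms about 30 patients per arm after dropout, which sets the scale in step 4. The 30 itself cannot be re-derived, because no effect size, standard deviation (SD) or power is given. The point does not depend on it.

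**2. Size of the error in one patient.** Let A be the study ulcer's initial area, B the neighbour's, r = B/A, and h the true proportional change in combined area. For two ulcers r is at most 1, because the study ulcer is the largest.

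- Scored with the rule: h
- Scored without it: (A + B)(1 + h)/A − 1 = (1 + r)(1 + h) − 1
- Difference: r(1 + h), or 100·r·(1 + h) percentage points
- On the cm² scale the difference is simply B

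**3. Examples (illustrative areas).**

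- 10 and 6 cm² merge to 18 cm². By week 4: (18 − 16)/16 = +12.5%. From week 5: (18 − 10)/10 = +80%. The gap is 67.5 points, which equals 100 × 0.6 × 1.125. In cm² it is +2 against +8.
- 10 and 5 cm² merge to 12 cm². By week 4: (12 − 15)/15 = −20%. From week 5: (12 − 10)/10 = +20%. The sign reverses.

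Score without the rule, by relative size of the neighbour:

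| True change h | r = 0.1 | r = 0.25 | r = 0.5 | r = 0.75 | r = 1 |
|---|---|---|---|---|---|
| −20% | −12% | 0% | +20% | +40% | +60% |
| 0% | +10% | +25% | +50% | +75% | +100% |

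**4. Effect on an arm of 30.** One late join with h = −20% moves the arm mean by 40/30 = 1.3 points at r = 0.5 and by 80/30 = 2.7 points at r = 1. In the 10 and 6 cm² example it is 67.5/30 = 2.25 points.

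**5. Effect on power.** Assume a share m of patients in both arms has a late join, J = 100·r·(1 + h) with h = −20%, two-sided alpha 0.05, and a difference sized for 80% power at 30 per arm. The inflated standard deviation is SD′ = √(SD² + m(1 − m)J²). For SD 30, m = 5% and r = 0.5: √(900 + 0.05 × 0.95 × 1600) = 31.2.

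| SD (points) | m = 5%, r = 0.5 | m = 10%, r = 0.5 | m = 10%, r = 1 |
|---|---|---|---|
| 30 | 77% | 74% | 59% |
| 50 | 79% | 78% | 71% |

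SD, m, r and h are assumptions; the documents give none of them.

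**6. Which areas are on file.**

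| Period | Study ulcer | Neighbour present at entry |
|---|---|---|
| Entry and first four weekly visits | recorded | recorded |
| After week 4, before a join | recorded | not required |
| After a join | traced as one merged wound | part of the merged wound |

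The entry areas needed to correct the baseline for a late join therefore exist. The neighbour's areas between week 4 and the join may not.

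**The case against.** The plan never says that a late join is scored as growth, and an assessor might try to trace only the original part of a merged wound. The four-week window also has a plausible origin: the literature review in section 1a notes that these ulcers commonly grow early in care, and the window matches the compulsory in-person visits and the period when every ulcer is measured. Late joins may be rare and neighbours small. At r = 0.1 with no true change the error is 10 points, and at m = 5% and r = 0.5 power falls only to 77–79%.

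Much of this stands. Frequency is unknown and size depends on the neighbour. But the plan does not give early growth as the reason for the window, and it would not justify scoring one event in two ways a week apart. Nothing provides for tracing part of a merged wound, so the single-ulcer baseline is the default.

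Three stronger readings are tempting but not supported:

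- *Early joins show false shrinkage, because a summed baseline is set against single-ulcer values in the preceding weeks.* Section 3h has all ulcers measured at the first four weekly visits, so those weeks can be summed. At most, a sentence saying so is missing.
- *The gap biases the comparison between arms.* That requires late joining to differ by dressing, and the documents give no evidence of it.
- *Extending the rule needs nothing further.* This holds for the baseline of ulcers present at entry. It does not hold for neighbours between week 4 and the join, or for ulcers that appear after entry.

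**Conclusion.** The point holds. Two sections limit the correction to four weeks of a 12-week follow-up, and under the plan as written a later join inflates the area change by 100·r·(1 + h) percentage points, or by the neighbour's initial area in cm². For two ulcers with no true change this ranges from almost nothing to a doubling.

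This rests on the single-ulcer baseline applying by default and, for the percentage figures, on change being expressed relative to baseline. Section 2 refers to reduction rates, while variable 10 is in cm². The total effect on the trial cannot be stated, because the frequency of late joins is not given. It adds noise, and adds bias only if late joining differs by arm. The change is worth making because it is cheap and the event is one the plan already foresaw.

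**What to change.** 1. Delete the four-week limit in sections 3c and 3h. For a join at any time through week 12, the outcome's baseline is the sum of the initial areas of the joined ulcers that were present at entry.
2. For visits before the join, use the summed component areas wherever they were recorded, which covers all of weeks 1 to 4. Treat unsummed visits between week 4 and the join as not comparable with the summed baseline.
3. For the ANCOVA covariate, use an area fixed at entry before randomisation, preferably the total of the study ulcer and its adjacent ulcers, with adjacency defined in advance. Extending item 1 alone would leave the covariate dependent on a later merge.
4. State separately how ulcers that arise after entry and then join are handled, since they have no initial area.

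Items 1, 2 and 4 cost a few sentences and no new measurement. Item 3 uses entry areas already planned, but needs a definition of adjacency and a record of which ulcers meet it. The price is some unusable weekly values between week 4 and a late join. A complete weekly series for the cluster would avoid that, but neighbouring ulcers would have to stay in the photo and be measured after week 4. That includes the photos which section 3h lets suitable patients send themselves, and which need show only the study ulcer.

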(3) Is the *improvised dressing* culturally acceptable to health care providers, patients, and families for managing SCLUs in Jamaica?

The expected study outcome is improvised dressing superior effectiveness and quality of life, when compared with usual practice, without increased safety and acceptability issues.^{13,59,60,62} The improvised dressing is likely to be the least expensive choice, with the added benefit of being available as first aid treatment throughout Jamaica. The advanced dressing is likely to be more expensive with respect to materials costs, although fewer dressing changes are anticipated and pain medication expenses are likely to be reduced. Based upon the review of the literature, no serious infections or other safety issues are anticipated for any group. However, to ensure that complications are not overlooked, in addition to the onsite researchers' vigilance, weekly wound photos will be assessed for complications (signs of infection, wound deterioration, or clinically relevant maceration) by two off-site blinded wound experts, Drs. [name] and [name].

Definitions:

Sickle cell leg ulcer – a wound in a HbSS or HbS β^0 positive patient, open greater than one month,⁷ below the level of the knee excluding the plantar surface of the foot.

Closed wound -100% epithelialized with no discernible scab or exudate production (paper napkin remains dry when lightly pressed against area, and no recurrence in the subsequent two weeks)

Safe – infection and other complications (healing-impairing maceration, keloid, and contracture rates) not statistically significantly higher than usual practice, with no major adverse events attributable to the method

Effective – ulcer closure rates or ulcer surface area reduction rates not statistically significantly lower than usual practice

Acceptable – average acceptability scores of 4 or higher on a 1-5 scale

3. Methods and Materials

a. Study design

This study will be a targeted-blinded (the off-site wound experts and the local physicians verifying wound closure and/or complications will be blinded to the randomization group), randomized controlled trial with three arms: (1) usual practice (negative control), (2) the improvised dressing, and (3) the advanced dressing (positive control). The expected outcome is improvised and advanced dressing superiority.

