- 2. Age of open wound prior to entrance into study (in weeks, patient/family report)
- 3. Previous ulcer treatments (if any)
- 4. Education level (in years)
- 5. Smoking or any use of nicotine (yes/no in past week)^{84,85}
- 6. Mid-arm circumference (a surrogate for nutritional status) 91,92
- 7. Initial area of SCLU in cm^2 (see methods for multiple adjacent SCLUs)
- 8. Initial depth of SCLU at deepest point, in cm
- 9. Anatomic location of SCLU
- 10. ASCQ-Me baseline scores (all measures see appendices)
- 11. Social isolation (lives alone, without nearby support)⁸⁶
- e. Inclusion and exclusion criteria

Inclusion Criteria:

- > Diagnosed with HbSS or HbS β^0 sickle cell disease
- > Ages 13 70 years at study initiation (able to comprehend and give consent)⁸²
- > Males and females, pregnancy is not an issue
- > Open wound below the knee, not including the plantar surface of the foot
- > Wound open for longer than one month (defined as a chronic SCLU)
- > Traumatic, spontaneous, or recurrent SCLU (all etiologies)

Exclusion Criteria:

- > Patient younger than 13 years of age at study initiation
- > Patient older than 70 years of age at study initiation
- Wound open for less than one month by conclusion of study enrollment period (acute wounds could be traumatic wounds unrelated to sickle cell diagnosis)
- ➤ Diagnosis of cancer, hypertension, or chronic renal failure⁸²
- ➤ Diabetes (will screen for undiagnosed diabetes)⁸²
- Active wound infection (evidenced by clinical signs of malodor, dark-colored or thick drainage, or significantly increased warmth at the periwound) which is not resolved by the conclusion of the study enrollment period
- Osteomyelitis (if osteomyelitis is suspected, an ESR will be drawn; > 70mm/h with high platelet levels and low serum albumin warrants a bone biopsy)^{93,94}

> Hydroxyurea use (may be a confound because it reduces inflammation and negates much of the pathology of SSD – may choose to abstain for the study)^{7,95}

f. Sampling

- i. All eligible participants who consent to the study will be included. Participants will be randomized into one of the three groups immediately after the initial cleansing/debridement of their SCLU by the nurse using an electronic random number generator (an app). Waiting until the study dressing is to be applied to generate the random number will provide allocation concealment.

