As a token of appreciation from the research team and an incentive for patients to return for their study clinic visits, each participant will be presented with a 500JM phone card at the end of each of the three 4-week study periods.

All wound management supplies for all three groups will be donated. Shipping and handling fees will be paid by the Principal Investigator with funds from a Wound Healing Foundation grant. Tallies of supplies used at dressing changes will be priced using the cost of medical supplies purchased by the SCU to determine the estimated cost of the treatment supplies for each patient. The PMD rolls will be valued at \$26.99US.⁹⁸

The Principal Investigator will de-identify the data and compile it from the patient Data Collection Tools onto an Excel spreadsheet. This spreadsheet and the de-identified wound photographs will be backed up onto the Principal Investigator's second password protected hard drive via a secure internet connection at least weekly. Two encrypted USB drives containing the data, including wound photographs, will be updated weekly on an alternating schedule and stored in a securely locked file in [name] office in UWI Department of Surgery.

i. Statistical analysis

A consultant, [name], PhD, Senior Biostatistician at The University of Texas Medical Branch in Galveston, will undertake the analysis.

When all of the patients have completed the study, the remainder of the data from the deidentified Data Collection Tools will be transcribed into an Excel spreadsheet by the Principal Investigator. The data will then be evaluated by the biostatistician using the most recent version of SPSS. Groups will be compared with respect to each of the 14 dependent variables, taking into account any confounding from the 11 independent variables. Results will be reported using descriptive statistics (means, modes, medians, frequencies), student's t test, and ANOVA with 95% CIs, using intent-to-treat.¹³ If the improvised dressing does not attain statistical superiority to usual practice, 80% CIs will be calculated with drop-outs removed from the analyses to evaluate noninferiority.^{13, Appendix: From Oczkowski SJW} Complications will be evaluated both individually and collectively by collapsing the pertinent columns.

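### The analgesic outcome has no unit or combination rule for non-opioid drugs, and no pre-randomisation analgesic dose is listed as a covariate, which costs precision on a supporting outcome

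*Combined protocol and SAP*

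**What the plan says.** Section 3d (Variables) lists 14 dependent variables. The third, among those measured weekly, is "Amount of pain medication taken, including a total number of morphine equivalents plus non-opioid pain medications". No unit, conversion table or combination rule is given for the non-opioid part.

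Section 3h (Data collection) has patients record "pain medication doses taken, time spent and supplies used at dressing changes" on a daily form that they are taught to use once enrolled. The named enrolment assessment of pain is a pain score: "Baseline persistent pain will be assessed using the Faces Pain Scale – Revised (FPS-R". Section 3h mentions no analgesic dose from before randomisation.

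None of the 11 independent variables in section 3d is an analgesic dose. The nearest are previous ulcer treatments and "ASCQ-Me baseline scores (all measures see appendices").

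In section 3i (Statistical analysis), "Groups will be compared with respect to each of the 14 dependent variables", and the ANCOVA controls for the independent variables. Section 2 says of the advanced dressing that "pain medication expenses are likely to be reduced".

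**The concern.** There are two gaps.

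**The definition.** An analyst who needs one number for variable 3 cannot derive it from the text. A milligram sum, a count of doses or tablets, and two separate endpoints are all open choices, and they can point in opposite directions. If the choice is made after the data are seen, the result is hard to defend.

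**The baseline.** The plan takes a starting value for ulcer area, ASCQ-Me and persistent pain, but lists none for analgesic use. Patients are likely to differ widely in what they already take, partly for sickle cell pain unrelated to the ulcer. Section 1a itself describes high opioid doses in this population. Without a prior dose in the model, those differences stay in the error term.

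Analgesic use also bears on how the pain scores are read. Participants are not blinded (section 5) and section 3h leaves pain prescriptions to usual protocol, so intake could differ by arm. Variable 3 is the listed measure that would show it.

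**Working it through.** **1. The plan's own figure.** Section 3f gives 90 participants, about 30 per group, and up to 120 recruited for 25% dropout: 90 / (1 − 0.25) = 120, as stated. The 30 per group cannot be reproduced, because no effect size, SD or power is given. Nothing in the sample size is tied to variable 3.

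**2. Direction of the score if the parts are summed.** All doses here are assumed and serve only as arithmetic. Let weekly opioid use fall from 420 to 210 mg morphine equivalents, starting with no non-opioid.

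| Non-opioid added (mg/week) | Raw sum before | Raw sum after | Opioid part alone |
|---|---|---|---|
| 200 | 420 | 210 + 200 = 410 | −210 |
| 210 | 420 | 210 + 210 = 420 | −210 |
| 3,500 | 420 | 210 + 3,500 = 3,710 | −210 |
| 7,000 | 420 | 210 + 7,000 = 7,210 | −210 |

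The break-even is 210 mg. Above it, halved opioid use scores as a rise in the sum. Reported alone, the opioid part has the right sign in every row.

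**3. Cost of the missing baseline.** Inputs: n = 30 per group (section 3f); two-sided 5% level, which is a reading of the 95% CIs in section 3i because sidedness is not stated; 80% power (assumed); correlation ρ between prior and on-study dose (assumed). Residual variance after adjustment is 1 − ρ² of the unadjusted value:

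- ρ = 0.5: 1 − 0.25 = 0.75, a cut of 25%, equivalent to 1 / 0.75 = 1.33 times as many patients.
- ρ = 0.8: 1 − 0.64 = 0.36, a cut of 64%, equivalent to 1 / 0.36 = 2.78 times as many patients.

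The smallest detectable standardised difference between two arms is (1.96 + 0.84) × √(2/30) × √(1 − ρ²):

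| ρ (assumed) | Detectable difference (SD) |
|---|---|
| 0 (no baseline) | 0.72 |
| 0.3 | 0.69 |
| 0.5 | 0.63 |
| 0.7 | 0.52 |
| 0.8 | 0.43 |

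These are upper limits on the gain, because the comparator is a model with no covariates. The planned ANCOVA already includes the ASCQ-Me baseline scores. To the extent that these predict dose, the extra gain is smaller. Recall error in the prior-week dose would lower ρ as well.

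**The case against.** Three stronger readings are tempting, and the documents support none of them.

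**That the plan will add the two classes into one score.** The wording can equally mean two components recorded together. Other numbered variables also have several parts: variable 5 is five ASCQ-Me short forms, and variables 12 to 14 each pair a Likert score with free text. A numbered variable in this plan is therefore not always one number, and the sign reversal holds only if someone sums. What stands is that the text does not rule this out and gives the non-opioid part no unit.

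**That without a baseline no reduction can be shown.** Variable 3 is the amount taken, not change; where change is meant, as in variable 10, the plan says so. A randomised comparison of amounts taken is unbiased without a baseline. Change from the first diary week is also available, although that week follows randomisation. What cannot be estimated from the listed variables is change from before randomisation.

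**That the plan hopes to move patients from opioids to simple analgesics.** Section 2 speaks only of lower medication expenses, and only for the advanced dressing.

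Two further points limit the weight. The enrolment form is in appendices that were not available and may record a prior dose; even so, that dose is not among the listed covariates. And analgesic use is not part of the definitions of safe, effective or acceptable, nor of the components listed in research question 2.

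**Conclusion.** The point holds as a cheap improvement. Variable 3 lacks a unit and a combination rule for its non-opioid part, and the listed ANCOVA covariates include no pre-randomisation analgesic dose. The consequences are an avoidable analytic choice and a loss of precision and of protection against chance imbalance. There is no bias in the comparison between arms.

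The size depends on the assumed correlation and power. Over the range 0.5 to 0.8, the gain forgone is at most a 25% to 64% cut in residual variance. The definition gap does harm only if raw amounts are summed. This is a supporting outcome: research question 1 rests on ulcer surface area, and the sample size does not change.

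**What to change.** 1. At enrolment, before randomisation, record all analgesic use over the previous 7 days, using the same lines as the daily form. Add it to the covariates for this outcome.
2. Replace variable 3 with two outcomes that are never summed: (3a) opioid dose in morphine equivalents per day, using one named conversion table; (3b) non-opioid use, as days or doses by drug class.
3. Fix the conversion table and the units before the data are analysed. Unblinding is not a usable marker here, because participants and the research team know the dressing.

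If the enrolment form already captures prior analgesic doses, step 1 reduces to naming them as a covariate.

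The cost is a change to the variable list and one short recall section at a visit that already takes place. Recall of a week's doses is less exact than the daily form. The change concerns measurement and analysis only; no treatment is altered.
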